5.4 Clobazam

Patients will use their own supply of Clobazam throughout the study. Clobazam usage will be recorded by the investigator. Clobazam is only an IMP for the blinded phase of the study.

6. PARTICIPANT ELIGIBILITY

Investigators will be required to maintain a log that includes limited information about all screened patients (initials, age, and gender; as allowed per local regulations) and outcome of screening.

6.1 Inclusion Criteria

For inclusion in the study patients must fulfil ALL of the following criteria:

- 6.1.1 Male or female patients aged 18 to 55 years inclusive.
- 6.1.2 Patient must have epilepsy as determined by the investigator and be taking CLB.
- 6.1.3 Patient must have a documented magnetic resonance imaging/computerized tomography of the brain that ruled out a progressive neurologic condition.
- 6.1.4 Patient must have experienced at least one seizure of any type (i.e., convulsive: tonic-clonic, tonic, clonic, atonic; focal: focal seizures with retained consciousness and a motor component, focal seizures with impaired consciousness focal seizures evolving to bilateral secondary generalization) within the two months prior to randomization.
- 6.1.5 Patients must be taking CLB and no more than two other AEDs during the course of the study.
- 6.1.6 AED(s), including CLB, must be stable for four weeks prior to screening and regimen must remain stable throughout the duration of the blinded phase of the study.
- 6.1.7 Intervention with vagus nerve stimulation (VNS) and/or ketogenic diet must be stable for four weeks prior to baseline and patient/caregiver must

be willing to maintain a stable regimen throughout the blinded phase of the study.

- 6.1.8 Patients must abstain from alcohol during the blinded phase of the study.
- 6.1.9 Patient and/or legal representative is available to attend all PK visits within the required visit window.
- 6.1.10 Patient and/or legal representative must be willing and able to give informed consent for participation in the study
- 6.1.11 Patient and/or legal representative must be willing and able (in the investigator's opinion) to comply with all study requirements.
- 6.1.12 Patient is willing for his or her name to be notified to the responsible authorities for participation in this study, as applicable.
- 6.1.13 Patient is willing to allow his or her primary care practitioner and consultant, if appropriate, to be notified of participation in the study.

6.2 Exclusion Criteria

The patient may not enter the study if ANY of the following apply:

- 6.2.1 Patient has clinically significant unstable medical conditions other than epilepsy.
- 6.2.2 Patients on CLB at doses above 20 mg per day.
- 6.2.3 Patients taking CLB intermittently as rescue medication.
- 6.2.4 Patient has a history of symptoms (e.g., dizziness, light-headedness, blurred vision, palpitations, weakness, syncope) related to a drop in blood pressure (BP) due to postural changes.
- 6.2.5 Any history of suicidal behavior or any suicidal ideation of type four or five on the C-SSRS in the last month or at screening.
- 6.2.6 Patient has had clinically relevant symptoms or a clinically significant illness in the four weeks prior to screening or enrollment, other than epilepsy.
- 6.2.7 Patient has consumed alcohol during the seven days prior to enrollment and is unwilling to abstain during the blinded phase of the study.
- 6.2.8 Patient is currently using or has in the past used recreational or medicinal cannabis, or synthetic cannabinoid based medications (including Sativex[®]) within the three months prior to study entry.
- 6.2.9 Patient has any known or suspected history of any drug abuse or addiction.
- 6.2.10 Patient is unwilling to abstain from recreational or medicinal cannabis, or synthetic cannabinoid based medications (including Sativex) for the duration for the study.
- 6.2.11 Patient has consumed grapefruit or grapefruit juice seven days prior to enrollment and is unwilling to abstain from drinking grapefruit juice within seven days of PK visits.
- 6.2.12 Patient has any known or suspected hypersensitivity to cannabinoids or any of the excipients of the IMP, e.g., sesame oil.

6.2.13 Female patient is of child bearing potential, or male patient's partner is of child bearing potential; unless willing to ensure that they or their partner use highly effective contraception for the duration of the study and for three months thereafter. Highly effective methods of contraception are defined as those, alone or in combination, that result in a low failure rate (i.e., less than 1% per year) when used consistently and correctly. Such methods include hormonal contraceptives, intrauterine devices/hormone-releasing systems, bilateral tubal occlusion, vasectomized partner or sexual abstinence.

6.2.14 Female patient who is pregnant (positive pregnancy test), lactating or planning pregnancy during the course of the study and for three months thereafter.

6.2.15 Patients who have received an IMP within the 12 weeks prior to the screening visit.

6.2.16 Any other significant disease or disorder which, in the opinion of the investigator, may either put the patient at risk because of participation in the study, may influence the result of the study, or the patient's ability to participate in the study.

6.2.17 Following a physical examination, the patient has any abnormalities that, in the opinion of the investigator would prevent the patient from safe participation in the study.

6.2.18 Patient has significantly impaired hepatic function at screening (Visit 1) or enrollment (Visit 2), defined as any of the following:

- Alanine aminotransferase (ALT) or Aspartate aminotransferase (AST) $>5 \times$ upper limit of normal (ULN).
- ALT or AST $>3 \times$ ULN **and** total bilirubin (TBL) $>2 \times$ ULN **or** international normalized ratio (INR) >1.5 .
- ALT or AST $>3 \times$ ULN with the presence of fatigue, nausea, vomiting, right upper quadrant pain or tenderness, fever, rash, and/or eosinophilia ($>5\%$).

*This criterion can only be confirmed once the laboratory results are available; patients randomized into the study who are later found to meet this criterion **must** be withdrawn from the study.*

6.2.19 Unwilling to abstain from donation of blood during the study.

6.2.20 Travel outside the country of residence planned during the study.

6.2.21 Patients previously enrolled into this study.

7. PATIENT ENROLLMENT

Before patients may be entered into the study, GW requires a copy of the relevant center's Ethics Committee (EC) or Institutional Review Board (IRB) written approval of the protocol, informed consent forms and other patient information material.

Patients will be considered enrolled in the study from the time of providing written informed consent. All patients, or legal representatives, where appropriate, must personally sign and date the consent form prior to any procedures being performed (refer to [Section 9.1.2](#) and [Section 15.2](#)).

7.1 Treatment Assignment

At the start of Visit 1, patients will be allocated a unique patient number, consisting of a four digit GW center number and a three digit patient identification number. The three digit patient number will be assigned in ascendant numerical order at each site. The unique patient number will be preceded by a unique letter. For example, P1234001, denoting patient 001 at site 1234. GWP will provide all GWP42003-P/placebo packed and labelled. Following enrollment at Visit 2, patients will be allocated a pre-packed numbered IMP.

7.2 Randomization

This is a double-blind study. Patients will be randomized in a 4:1 ratio to receive 20 mg/kg GWP42003-P or placebo.

8. TREATMENT PROCEDURES

8.1 Investigational Medicinal Product Dosage, Administration and Schedule

The IMP will consist of three types of medication:

- GWP42003-P Oral Solution containing 100 mg/mL CBD.
- Placebo Oral Solution containing excipients.
- Clobazam (patient supplied).

The GWP42003-P/placebo will be presented as an oral solution containing either the active pharmaceutical ingredient and excipients (in the case of GWP42003-P) or only excipients (in the case of placebo). For details regarding GWP42003-P/placebo formulations, see [Section 5](#).

All patients will be weighed during the study visits and the daily volumes of GWP42003-P/placebo solution to be taken during the titration period, and for the remainder of the study, will be calculated and provided to the patient and/or caregiver. Further information on dispensing procedures will be provided in a separate Pharmacy Manual.

Each patient will take their first dose of GWP42003-P/placebo at Visit 2, Day 2 in the clinic. Patients not entering the OLE will take their final maintenance dose of GWP42003-P/placebo at Visit 4 (Day 33) in the clinic. Patients entering the OLE will take their final dose of IMP at Visit 11 (one year after the end of the blinded phase of the study) or sooner (if marketing authorization is granted within one year).

Patients will use their own supply of Clobazam throughout the study. Patients will continue on the dose that they were on at screening for the blinded phase of the study. Clobazam will only be an IMP for the blinded section of the study.

8.1.1 Dose Administration

GWP42003-P/placebo will be administered orally by the patient or their caregiver twice each day (morning and evening) using the syringe(s) provided.

GWP42003 P/placebo should be taken immediately after the patient's usual CLB administration. The GWP42003-P/placebo should be swallowed, as per the intended commercial therapeutic route, and may be taken with other concomitant medications, as directed by the investigator.

8.1.2 Dose Escalation and Dose Adjustments

Patients will enter the blinded phase of the study and will be up-titrated over ten days (Day 2 to Day 11) to a maintenance dose or equivalent of GWP42003-P/placebo of 20 mg/kg/day. If GWP42003-P is not tolerated then the dose can be reduced accordingly at the discretion of the investigator. The titration regimen is described in [Table 8.1.2-1](#).

Table 8.1.2-1 Dose Up-Titration Regimen*		
Day - GWP42003-P/Placebo (Blinded Period)	Day - GWP42003-P only (OLE**)	Dose Level (GWP42003-P or equivalent placebo)
2	34	2.5 mg/kg
3	35	2.5 mg/kg
4	36	5.0 mg/kg
5	37	5.0 mg/kg
6	38	7.5 mg/kg
7	39	7.5 mg/kg
8	40	10.0 mg/kg
9	41	10.0 mg/kg
10	42	15.0 mg/kg
11	43	15.0 mg/kg
12 onwards	44 onwards	20.0 mg/kg

*GWP42003-P /placebo is to be taken twice daily. Total daily doses are shown.

** Only patients who were taking placebo during the double-blind period will up-titrate according to this schedule during the OLE period. Those taking GWP42003-P during the double-blind period will down-titrate their blinded IMP whilst simultaneously up-titrating with GWP42003-P, thus maintaining a daily dose of 20 mg/kg/day GWP42003-P throughout.

The titration regimen defined above should be followed to the maximum dose (20 mg/kg/day). Should an AE occur during titration which is attributable to IMP or concomitant AED, then IMP dose should be reduced to the next lower dose. Any other changes in concomitant AED therapy should be reviewed with the medical monitor before being initiated.

For those patients who do not enter the OLE the dose of GWP42003-P/placebo will taper off over 10 days beginning on Day 34. The patient will reduce the dose by 10% of the maintenance dose each day and treatment will end on Day 43.

Patients who enter the OLE period will be transitioned to the OLE treatment over a 10-day period in order to maintain blinding, simultaneously down-titrating blinded GWP42003-P /placebo whilst up-titrating open-label GWP42003-P. As such, patients who were taking GWP42003-P during the blinded period will maintain their 20 mg/kg/day dose throughout the transition from the blinded period into the OLE period and patients who received placebo during the blinded period up-titrate slowly to the 20 mg/kg/day dose in the OLE period. After this has taken place, the

maintenance dose of GWP42003-P may be adjusted up or down at the discretion of the investigator to a maximum of 30 mg/kg/day (no minimum).

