8.2 Concomitant Therapy

Doses of any concomitant AEDs, including CLB, must have been stable for at least four weeks prior to screening and must remain stable throughout the blinded phase of the study. If there are symptoms of toxicity suspected to be from a drug interaction, the investigator may adjust GWP42003-P/placebo or the CLB or other AEDs after discussion with the medical monitor.

The use of rescue medication is allowed if necessary. The use of oxygen may be considered as rescue medication if used as required. Any medication, other than the IMP, taken during the study must be recorded on the Case Report Form (CRF).

Any non-pharmacological therapies (e.g., ketogenic diet, VNS) must also be stable up to four weeks prior to baseline and throughout the duration of the study.

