9.2.1.4.2 Visit 4 (Day 34)

This is the second part of the two day visit. The final PK sample will be collected 24 hours after the Day 33 morning CLB dose.

Following completion of the PK sampling process the following observations will be made on Day 34: concomitant medications (including AEDs), physical examination (including body weight), vital signs and AEs.

At the end of the blinded phase of the study on Day 34, providing the investigator and patient both agree, patients will be invited to continue taking GWP42003-P and to enter the OLE.

Patients who enter the OLE will be dispensed GWP42003-P on Day 34. At the point of entry to the OLE, patients will be transitioned to the OLE treatment over a 10 day period in order to maintain blinding. The dose may be adjusted up or down by the investigator from the maintenance dose of 20 mg/kg/day in the blinded phase to a maximum of 30 mg/kg/day in the OLE. Patients and/or their caregivers will be provided with individual dosing schedules as described in [Section 8.1.2](#). Patients, or their caregivers, will be instructed how to record the diary information.

Patients who do not enter the OLE will begin a 10 day taper period during which they will taper off their daily dose of GWP42003-P/placebo. The daily dose will be reduced by 10% of the maintenance dose per day and treatment will end on Day 42.

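### Section 8.1.2 allows dose reduction in the blinded phase, but its OLE transition text assumes every GWP42003-P patient is still on 20 mg/kg/day

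*Protocol*

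**What the plan says.** **Reduction in the blinded phase.** Section 8.1.2 sets a target of 20 mg/kg/day after titration on Days 2 to 11, with two routes to a lower dose. The general one is "If GWP42003-P is not tolerated then the dose can be reduced accordingly at the discretion of the investigator". The second covers an adverse event during titration that is attributed to IMP or a concomitant AED: "then IMP dose should be reduced to the next lower dose". The only medical-monitor step in 8.1.2 is "Any other changes in concomitant AED therapy should be reviewed with the medical monitor before being initiated".

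**Transition to the OLE.** Section 8.1.2 withdraws blinded product over 10 days while open-label GWP42003-P is raised. It says that patients who had GWP42003-P in the blinded period "will maintain their 20 mg/kg/day dose throughout the transition from the blinded period into the OLE period". The footnote to Table 8.1.2-1 says the same: "thus maintaining a daily dose of 20 mg/kg/day GWP42003-P throughout". Only once this is complete does the section say that the "maintenance dose of GWP42003-P may be adjusted up or down at the discretion of the investigator to a maximum of 30 mg/kg/day".

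**Visit 4, Day 34.** Section 9.2.1.4.2, and the synopsis in matching words, state: "The dose may be adjusted up or down by the investigator from the maintenance dose of 20 mg/kg/day in the blinded phase". Section 9.2.1.4.2 gives no timing for that adjustment and sends sites to 8.1.2 for the individual dosing schedules.

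**Suspected interaction toxicity.** Section 8.2 says that "the investigator may adjust GWP42003-P/placebo or the CLB or other AEDs after discussion with the medical monitor".

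**The concern.** The section that creates reduced-dose patients contains no transition rule for them. Its OLE text is true only of a patient who reached and kept 20 mg/kg/day. For anyone else it is inaccurate as a description. Because sites draw their dosing schedules from it, it can also work as an instruction.

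What is at stake is patient safety at OLE entry. A patient held below target because the product was not tolerated could, by default, be brought back to the full target dose during a period with no scheduled clinic visit, under a text that places adjustment at the end of that period. The primary comparison is not at stake: the last sample of the second PK profile is taken on Day 34, before the transition begins.

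There is a smaller wording problem. Suspected interaction toxicity can fall under both 8.1.2, which has no monitor step for reducing GWP42003-P/placebo, and 8.2, which mentions discussion with the monitor and names that product too.

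**Working it through.** No sample size, power or alpha figure is involved, so there is no stated figure to reproduce. The check is dose arithmetic on the protocol's own schedule.

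**Inputs**
- Open-label column of Table 8.1.2-1 (8.1.2), total mg/kg per day: Days 34–35, 2.5; Days 36–37, 5; Days 38–39, 7.5; Days 40–41, 10; Days 42–43, 15; Day 44 onwards, 20.
- Possible reduced doses D, taken from the same ladder: 15, 10, 7.5 and 5 mg/kg/day.
- First OLE clinic visit (9.2.2.1): two weeks after Visit 4 (Day 34), ± 3 days.

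**Assumption A.** The open-label column applies to both arms. The footnote assigns that column to former placebo patients only. It says former GWP42003-P patients up-titrate open-label drug while blinded drug is taken down, but gives them no day-by-day schedule. One common schedule is a natural inference from the stated aim of keeping the blind, but it is an inference.

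**Dose on Day 44 relative to the reduced dose** (blinded product fully withdrawn)

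| Reduced dose D | 20 / D | First day open-label drug alone exceeds D |
|---|---|---|
| 15 | 1.33 | Day 44 |
| 10 | 2 | Day 42 |
| 7.5 | 2.67 | Day 40 |
| 5 | 4 | Day 38 |

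**Path during the transition.** No blinded down-titration table is given, so a second assumption is needed. Assumption B cuts blinded product in proportion to the open-label increase: total = D × (1 − o/20) + o, where o is the open-label dose.
- D = 20: the total is 20 on every day, so the text works for this patient.
- D = 15: 15 × (1 − 2.5/20) + 2.5 = 15.6 on Day 34; 15 × (1 − 15/20) + 15 = 18.75 on Day 43; 20 on Day 44.
- D = 10: 11.25 on Day 34; 17.5 on Day 43; 20 on Day 44.
- D = 5: 6.9 on Day 34; 16.25 on Day 43; 20 on Day 44.

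If blinded product is instead cut by 10% of D per day, it reaches zero on Day 43 and the total is again 20 on Day 44 for every D. The Day 44 result therefore depends on Assumption A but not on B.

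**Timing of the first check.** 34 + 14 = 48; ± 3 days gives Days 45 to 51. Then 45 − 44 = 1 and 51 − 44 = 7, so 20 mg/kg/day is reached 1 to 7 days before the first OLE visit.

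**Who could be affected.** 4:1 randomization of 20 patients gives 20 × 4/5 = 16 on GWP42003-P and 4 on placebo. The protocol gives no figure for how many would be reduced and remain so at Visit 4.

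**The case against.** The strongest answer is that the investigator stays in control. Section 4.1 leaves OLE dosing to the investigator's advice. Section 3.3.1 allows OLE doses to go up or down on the investigator's opinion, with no restriction to the period after the transition. Section 9.2.1.4.2 makes OLE entry depend on the investigator's agreement and permits adjustment. The sentence on keeping 20 mg/kg/day can also be read as describing the patient at target rather than ordering a reduced patient upwards. All of this stands, so a reader who infers a mandatory overdose goes too far. It does not repair the default, however: 9.2.1.4.2 itself takes 20 mg/kg/day as the blinded-phase dose and refers back to 8.1.2.

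Other stronger readings are tempting but not supported:
- *Section 8.2 blocks a safety reduction.* It does not. Its wording is permissive, 8.1.2 gives discretion, and section 11 allows urgent safety measures. The overlap arises only where interaction toxicity is suspected.
- *The IMP to be stepped down might be clobazam, since 8.1 lists it as an IMP.* The dose ladder in Table 8.1.2-1 and the rationale in section 3.3.2 of Amendment 1 show that GWP42003-P/placebo is meant.
- *Nothing is said about resuming titration.* Section 8.1.2 says the regimen should be followed to the maximum dose. That gives a direction, though no timing.
- *A step-down undermines the second PK profile.* The Visit 4 window already accepts 30 − 12 = 18 to 36 − 12 = 24 maintenance days. An assumed two-day hold with the level repeated, so that 20 mg/kg starts on Day 15 or 16, would leave 33 − 15 = 18 or 33 − 16 = 17 at Day 33. That loss is small.

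**Conclusion.** The point holds as a defect in the written OLE default. Section 8.1.2 permits reduced doses and then treats every GWP42003-P patient as being on 20 mg/kg/day through a transition after which adjustment is placed. Under Assumption A, a patient left on 15, 10, 7.5 or 5 mg/kg/day would be at 1.33 to 4 times that dose on Day 44, before any scheduled OLE visit. Without Assumption A the day-by-day path cannot be derived, but the statement that such a patient maintains 20 mg/kg/day is still untrue. The investigator can override the default, and the number affected is unknown. It should be corrected because the correction is cheap and concerns patients who did not tolerate the full dose.

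The overlap between 8.1.2 and 8.2 needs an editorial clarification only.

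**What to change.** **Section 8.1.2, OLE paragraph and table footnote.** State that patients maintain the dose level in use at Visit 4 (20 mg/kg/day unless reduced), that open-label up-titration stops at that assigned level in both arms, and that the investigator may adjust the dose during the transition if needed. The assigned level is known for both arms, as drug or equivalent placebo, so the blind holds. Blinded decrements should match open-label increments so that the total stays constant.

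**Synopsis (Visit 4, Day 34) and section 9.2.1.4.2.** Add *unless reduced* after the 20 mg/kg/day blinded-phase dose.

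**Section 8.2, clarification.** State that an immediate safety reduction of GWP42003-P/placebo under 8.1.2 need not wait for the medical monitor, who is informed promptly, while changes to CLB or other AEDs need prior discussion. This keeps the monitor involved; removing that step altogether would be an oversight decision that the protocol does not settle.

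**Cost.** A few sentences, with no change to visits, samples, day numbering, Visit 4 or the maintenance period. The drawback is that a placebo patient on a reduced volume (about 4 of the 20 are on placebo) starts the OLE at a lower open-label dose until it is adjusted.

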8.2 Concomitant Therapy

Doses of any concomitant AEDs, including CLB, must have been stable for at least four weeks prior to screening and must remain stable throughout the blinded phase of the study. If there are symptoms of toxicity suspected to be from a drug interaction, the investigator may adjust GWP42003-P/placebo or the CLB or other AEDs after discussion with the medical monitor.

The use of rescue medication is allowed if necessary. The use of oxygen may be considered as rescue medication if used as required. Any medication, other than the IMP, taken during the study must be recorded on the Case Report Form (CRF).

Any non-pharmacological therapies (e.g., ketogenic diet, VNS) must also be stable up to four weeks prior to baseline and throughout the duration of the study.

